8.9 Concomitant Medication

Concomitant medication is defined as any medication used by a subject during the clinical trial apart from the investigational product. Concomitant medication including diagnoses must be recorded in the medical record and the eCRF at visits specified in section 8.1.

8.10 Pregnancy Test

A urine pregnancy test must be performed at the trial site in female subjects of child-bearing potential at visits specified in section 8.1.

8.11 Laboratory Assessments

8.11.1 Urine collection for pregnancy test

Qualitative urine pregnancy test (dip-stick) of human chorionic gonadotropin (HCG) must be performed as scheduled in section 8.1. The test will be performed locally.

8.11.2 Microbiome and Biomarker

Collection is described in [Appendix 2](#) and [Appendix 3](#). Handling and shipment instructions for the samples are provided in a separate laboratory manual.

8.12 Adverse Events

AEs must be assessed and recorded as specified in section [9](#).

8.13 Other Safety Assessments

Local Skin Responses (LSRs)

Assessment of local skin responses in the treatment areas using the LSR Grading Scale will be performed at Day 1 prior to first IP application and at all subsequent visits as indicated in section [8.1](#).

Local skin responses are defined as erythema, flaking/scaling, crusting, swelling, vesiculation/pustulation and erosion/ulceration. The presence/absence and grade of each LSR will be recorded using the LSR Grading Scale shown in [Appendix 6](#). This grading scale will also be provided as hard copy to the site. Any local skin responses identified within the treatment area which do not match the criteria in the LSR Grading Scale should be reported as AEs.

8.14 Subject Reported Outcomes

The subject must complete Acne-QoL at Visit 2 (Day 1) and Visit 10 (Week 12, End of Trial).

The subject must complete TSQM II and Subject Global Cosmetic Score at Visit 10 (Week 12, End of Trial).

Subject-reported outcome measures should be completed prior to any other assessments at the respective trial visits in the following order: Acne QoL, TSMQ II and Subject Global Cosmetic Score. The subjects should be encouraged to answer all questions in the questionnaires.

8.15 Investigator Assessments

The investigator assessments will be conducted by an experienced and qualified dermatologist. All assessments of each subject at the site should preferably be performed by the same dermatologist. At Visit 1, identification of the treatment area should be documented on an individual transparent film using three-point landmark technique (refer to [Appendix 10](#)

for details). At all subsequent visits, the transparent film should be used to locate the treatment area for further treatment or assessments of the treated skin.

The following clinical assessments must be made at visits as specified in section 8.1:

1. IGA of the full face (see Table 4 for grading) at Screening to determine acne vulgaris severity for inclusion to the trial at Screening.
2. IGA and non-inflammatory lesion count (open and closed comedones), and inflammatory lesion count (erythematous papules and pustules) in TA_{left} and TA_{right} at Screening and Day 1, Week 2, 4, 8, and 12.
3. LSR assessments (see 8.13) in TA_{left} and TA_{right} using the LSR Grading Scale at Day 1 prior to IP application, and on all subsequent site visits.
4. Skin photography at Day 1, prior to treatment, and on all subsequent site visits (only for cohort 1, 2, and 3).
5. Skin photography at screening for cohort 3 and 4
6. All other skin findings than LSRs and acne will be reported as medical history at Screening or as AEs at subsequent visits.
7. Biomarker and microbiome samplings in Cohort 2, 3 and 4 at Day 1 and at Week 2, 4, 8 and 12. See [Appendix 2](#) and [Appendix 4](#). Samples will be stored for later analysis.

Table 4. Investigator's Global Assessment Scale for Acne Vulgaris*

Grade	Description
0	Clear skin with no inflammatory and non-inflammatory lesions
1	Almost clear; rare non-inflammatory lesions with no more than one small inflammatory lesion
2	Mild severity; greater than Grade 1; some non-inflammatory lesions with no more than a few inflammatory lesions (papules/pustules only, no nodular lesions)
3	Moderate severity; greater than Grade 2; up to many non-inflammatory lesions and may have some inflammatory lesions, but no more than one small nodular lesions
4	Severe; greater than Grade 3; up to many non-inflammatory and inflammatory lesions, but no more than a few nodular lesions

*The same scale will be used for full face and TA evaluation of IGA.

8.16 Dispensing of IP

Not applicable as this is an investigator applied IP.

8.17 Return of IP and Compliance

Refer to Sections [10.7.1](#) and [10.7.3](#).

8.18 End of Trial Form

The End of Trial Form must be completed for all subjects who have signed informed consent. This includes e.g. date of last dose, last attended scheduled visit number, primary reason for withdrawal, etc.

9 Adverse Events

- AEs and serious AE (SAEs) are defined in [Appendix 7](#).
- Classification of adverse events in terms of severity, causality and outcome are defined in [Appendix 8](#).

9.1 Collection of Adverse Events

AEs must be collected from the time of first trial-related activity after the signing of the informed consent form until last visit at Week 12.

Abnormal findings observed at the screening visit should be recorded as diagnoses in the Concomitant Medication page if medication is currently being taken for the condition. If not, it will be documented as medical history in the eCRF.

AEs must be assessed by medically qualified personnel. A qualified and experienced dermatologist must conduct all dermatologic examinations, LSR and AE evaluations of the treatment areas.

For AEs recorded on the day starting treatment, it should be specified whether the AE started prior to or after first application of IP.

At all visits, the subject will be asked a non-leading question by the (sub)investigator about AEs, for example: “How have you felt since I saw you last?”. No specific symptoms should be asked for. It is important that the (sub)investigator also observes the subject for any changes not reported by the subject and records these changes.

9.1.1 Local Skin Responses

Local Skin Responses which match the criteria in the LSR Grading Scale are to be reported on the Local Skin Response sections in the eCRF and not as AEs in the eCRF even if they require treatment. Skin responses other than those identified in the LSR scale must be recorded appropriately as AEs.

Any LSRs classified as a SAE must be added to the AE form and in addition be reported to LEO on the SAE Form (according to “Investigator Reporting Responsibilities”, section 9.4.1)

Any treatment for a LSR must be recorded on the concomitant medication page of the eCRF with the most important LSR (e.g. swelling should be reported as swelling-LSR).

9.2 Reporting of Adverse Events in the eCRF

AEs reported by the subject or observed by the (sub)investigator must be recorded on the adverse event form of the eCRF and should be described in the following manner:

The *AE term* will be in precise English medical terminology (i.e. not necessarily the exact words used by the subject). Whenever possible, a specific diagnosis should be stated (e.g. allergic contact dermatitis).

For AEs, the location must be part of the adverse event description and may be described as “in the treatment areas”, “outside the treatment areas” or “not applicable”. For adverse events in treatment areas the lateral side needs to be specified also.

The *duration* of the AE must be reported as the start date and stop date of the event. In addition, it must be recorded whether the AE started prior to start of trial medication.

AEs must be classified in terms of severity, causality and outcome according to the definitions in [Appendix 8](#).

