Women of childbearing potential must have a urine pregnancy test performed.

In Cohort 2, 3 and 4, non-invasive samples from the skin will be taken for evaluation of inflammatory markers, skin microbiome profile (For details see Appendix 2 and Appendix 4).

Subjects in Cohort 1, 2 and 3 will be photographed at all site visits from Day 1 and onwards for documentation of physical appearance (Appendix 3). Photographs will be taken at screening for Cohort 3 and 4 for documentation of eligibility.

Each subject will be left/right randomised to receive active treatment on TA_{left} or TA_{right}. The other side will be treated with vehicle gel.

Treatment Phase (Day 1, 2 and 3)

During the treatment phase, trial visits will be performed on Day 1, Day 2 and Day 3.

The individual transparent film(s) will be used to locate the TAs.

LSR scores for the TAs will be recorded and any new or on-going AEs, and changes in medication will be recorded.

Criteria for treatment on Day 2 and Day 3:

- The subject not reporting intolerable response to treatment.
- The (sub)investigator not evaluating LSRs or treatment-related AEs to be unacceptable.
- The LSR scores not exceeding predefined criteria (see Table 1).

Table 1. LSR score criteria for not administering second or third treatment.

LSR component(s)	Score on Day 2 and/or 3
Erosion/ulceration	≥2
Vesiculation/pustulation	≥3
Any LSR component	=4
Flaking/scaling + crusting	≥5 (sum)
Flaking/scaling + crusting + vesiculation/pustulation	≥6 (sum)

The reason not to treat is recorded in the eCRF. Subjects will remain in the trial and attend the follow-up visits according to the protocol.

The IPs are to be applied to the TAs by the site staff as per the randomization schedule at all three treatment visits (Visit 2, 3 and 4). Subjects will be carefully instructed in how long the IP must remain on the skin and how it can be washed off. Moreover, the subjects will be reminded about the precautions regarding accidental transfer of the IP to eyes and other areas (refer to section 10.3.2).

Post-treatment assessment (Day 2, 3, 4 and 8)

If the subject is not treated on Day 2 or Day 3, trial procedures will follow the trial schedule as described in Section 8.1. LSR scores for the TAs will be recorded and any new or ongoing AEs, and changes in medication will be recorded in the eCRF.

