10.2 Administration of Investigational Products

Route of administration	Topical administration
Application range	Left and right cheek treatment areas (TA _{left} and TA _{right}) corresponding to approximately 36 cm ² each.
Application frequency	Once daily for up to three consecutive days
Daily maximum	Approximately 1/3 of a tube per TA applied by the trial staff as a thin wet layer.
Time of day for application	No specific requirements
Relation of time of application to dietary intake	No specific requirements

The IP will be applied to the treatment areas at the clinic by the trial site staff .

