10.3 Precautions/Over dosage

10.3.1 Skin exposure

The most common LSRs reported in the AK studies with LEO 43204 gel are erythema, flaking/scaling, and crusting. Less common LSRs include swelling/oedema, vesiculation/pustulation, and erosion/ ulceration. Completed clinical trials have shown LSRs to be transient and normally resolved within two weeks (please refer to the Investigator's Brochure of LEO 43204 gel in Actinic Keratosis Edition 4 or any updates hereof for further details).

In a low percentage of subjects treated on face or scalp, swelling around the eyes or on the eyelids may develop to a point where it may be considered clinically significant. In such cases these AEs should be recorded as peri-orbital oedema or eyelid edema. Treatment is usually straightforward with cold compress on the eye(s) with the subject resting in supine position for a few hours.

The mean maximum composite LSR score in Part 2 of LP0084-1013 (face) for the doses of LEO 43204 gel that will be used in the current trial was 8.9 for face. Using the same doses for 3 consecutive days (LP0084-1148), mean maximum composite scores were 10.6 for face. Peak value in the LP0084-1013 trial (face) was at Day 3. At Day 15, mean maximum composite LSR score was either at baseline value or close to baseline value in almost all subjects treated on face (refer to the Investigator's Brochure of 43204 gel in Actinic Keratosis Edition 4 or any updates hereof).

Investigators conducting clinical trials with LEO 43204 gel should ensure that investigational site staff is trained in the protocol-specified application procedure(s) and follow appropriate precautions. Investigators must monitor their subjects for the emergence and resolution of LSRs and AEs

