11.3.8 Adverse Events

Treatment emergent adverse events, i.e. with an onset or intensifying after treatment start will be coded according to MedDRA v19.0 summarised by the following tables showing event counts, incidences and incident rates:

- An overall summary showing statistics for all AEs, serious AE's, AE's with actions taken, AE's stratified by severity, related AE's by treatment, cutaneous AE's by treatment
- AE by system organ class and preferred term
- AE's by system organ class and preferred term stratified by disease severity
- Related AE's by system organ class and preferred term by treatment
- Cutaneous AE's by system organ class and preferred term by treatment
- Serious adverse events will be evaluated separately and a narrative for each will be given.
- AEs leading to withdrawal from trial or discontinuation of investigational product will be listed.

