4.4.1 Adverse Events

The treatment emergent adverse events will be tabulated in the following categories:

- Cutaneous
 - Outside of treatment area
 - Leo 43204 Gel 0.018%
 - Vehicle
- Non-cutaneous

The split between cutaneous and non-cutaneous will be based on the MedDRA preferred term text as follows:

- Cutaneous
 - Application site plain
 - Application site pruritus
- Non-cutaneous

- Headache
- Nausea

Frequencies, incidences and incidence rates for treatment emergent adverse events will be presented in the following tables

- Overall summary table of adverse events
- Adverse events presented by system organ class and preferred term
- Adverse events presented by system organ class and preferred term and severity
- Related adverse events presented by system organ class and preferred term

All adverse events will be listed split by treatment emergent and non-treatment emergent. Adverse events leading to withdrawal or discontinuation of treatment will be listed.

A listing of unacceptable LSR events, following section 11.3.10 in the protocol, and LSR scores for not administering the 2nd or 3rd treatment (table 1 in protocol) will be shown together with reason for no treatment.

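### Side of face is not required for adverse events outside the cheek areas, so anticipated periorbital or eyelid oedema need not be attributable to LEO 43204 or vehicle

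*Protocol*

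**What the plan says.** Treatment is allocated within the face. Protocol 6.1: "Each subject will be left/right randomised to receive active treatment on" one of two areas, with vehicle on the other. Section 10.2 gives the application range as "Left and right cheek treatment areas" of about 36 cm² each.

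For adverse events (AEs), Protocol 9.2 says that "the location must be part of the adverse event description and may be described as" inside the areas, outside them, or not applicable. It then adds: "For adverse events in treatment areas the lateral side needs to be specified also". It has no matching rule for events elsewhere on the face.

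Protocol 10.3.1 warns that in some subjects treated on the face or scalp, "swelling around the eyes or on the eyelids may develop to a point where it may be considered clinically significant". It continues: "In such cases these AEs should be recorded as peri-orbital oedema or eyelid edema". No side is asked for.

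On tabulation, Protocol 11.3.8 plans "Cutaneous AE's by system organ class and preferred term by treatment" and a matching table for related AEs. Neither is limited to the treatment areas. SAP 4.4.1 divides cutaneous AEs into three categories: "Outside of treatment area", LEO 43204 gel and vehicle. Non-cutaneous AEs form one category with no treatment split.

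**The concern.** In a parallel-group trial every AE belongs to an arm through the subject. Here each subject receives both products, so a local event belongs to a product only through its side. The causality rating cannot replace side: Appendix 8 rates relation to the investigational product as a whole, and the assessor is blinded to which cheek received active gel.

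The capture rule stops at the edge of the cheek areas, while the protocol itself anticipates a facial reaction beyond that edge. The secondary objective is the safety and tolerability of the two gels, and sections 3.3.1 and 3.4 say that the reaction profile in young adults with acne is unknown. If an eyelid or periorbital event occurs, the plan does not ensure that a reader can tell which product was on that side. The planned tables would not show it even if side had been noted.

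**Working it through.** The protocol and SAP state no figure on this point, so the check is to follow each kind of local event from recording to table.

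| Event | Recorded as | Side required? | Reaches a treatment column? |
|---|---|---|---|
| Reaction in the cheek area that fits the LSR scale | LSR, not AE (9.1.1) | Yes, scored per area (8.15) | Yes (11.3.9.1) |
| Contiguous spread past the border that fits the LSR scale | LSR grade 4 (Appendix 6) | Yes | Yes |
| Other cutaneous AE in the cheek area | AE | Yes (9.2) | Yes (SAP 4.4.1) |
| Discrete cutaneous AE on the face, outside the area | AE | No | No, pooled category |
| Clinically significant periorbital or eyelid oedema | AE (10.3.1) | No | No, whichever class it falls in |

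1. Second row: in Appendix 6, grade 4 of erythema, flaking/scaling, crusting, swelling and vesiculation/pustulation is defined by extension outside the treatment area. That is five of six components; erosion/ulceration is the exception. Most spread across the border is therefore already captured by side.
2. Last row: the SAP separates cutaneous from non-cutaneous by preferred term and gives four example terms, none of them oedema. If the event is classed as cutaneous, it goes to the pooled outside category. If not, it goes to a category with no treatment split.
3. Consistency: Protocol 11.3.11 asks that changes to the planned analysis be described and justified. The SAP does this when it replaces Fisher's exact test with McNemar's test. It gives no such note for the events that 11.3.8 would show by treatment and SAP 4.4.1 does not.
4. Other sources of side: cohorts 1 to 3 (3 + 6 + 6 = 15 subjects) have left, frontal and right photographs at every site visit from Day 1. Cohort 4 (25 of 40 subjects) is photographed only at screening. Its Day 8 contact is a phone call with no scheduled LSR evaluation, so at that time point the AE report is the scheduled record.
5. Size: the protocol says only that the share of subjects with such swelling is low. Purely as an assumption, 2% to 10% of 40 subjects is 0.02 × 40 = 0.8 to 0.10 × 40 = 4 subjects. The finding does not rest on this range.

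**The case against.** The strongest reply is that the trial's main local-tolerability measure already does the work. LSRs are scored separately on each side and summarised by treatment, and the grade 4 definitions cover spread beyond the area. This stands. A reader might infer that reactions just past the cheek border are lost and that the AE tables therefore understate the active side. The documents do not support that. Contiguous spread that fits the scale goes to the LSR pages by side, and nothing shows which side the remaining events would favour.

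A reader might also infer that out-of-area events can never be attributed. That too goes beyond the text. Section 9.2 sets a minimum and does not forbid adding side to the description. The eCRF and table shells are not among the documents. Serious AEs receive narratives, all AEs are listed, and side may be recoverable from source records or, for 15 subjects, from photographs.

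A third reply is that side is an imperfect key outside the areas. Swelling may be bilateral or midline, and transferred gel can cross the face, so a separate category is a cautious choice. This stands for those events. It does not justify leaving side unrecorded for clearly one-sided events or pooling them with events elsewhere on the body. The cheek swelling score is only indirect evidence of which eye was affected, because 10.3.1 sends clinically significant eye swelling to the AE form under its own term.

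Finally, the AE tables are descriptive, the primary endpoint is untouched, and the safety committee reviews blinded data by subject. All of this is true, and it limits the weight of the point.

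**Conclusion.** The point holds for a narrow class: discrete facial AEs outside the cheek areas that are not graded as LSRs, chiefly clinically significant periorbital or eyelid oedema. For these, side is not required at capture and SAP 4.4.1 provides no treatment column, while Protocol 11.3.8 plans related and cutaneous AEs by treatment without that restriction. They need not be attributable to either gel.

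The number of subjects affected is unknown. The 0.8 to 4 of 40 shown above rests on an assumed 2% to 10%. The protocol's remark about a low share concerns subjects treated on the face or scalp, in a section that draws on the actinic keratosis studies, so it may not carry over to cheek areas in acne. Two further assumptions are that the eCRF follows 9.2 as written and that the table shells follow SAP 4.4.1. The matter is worth correcting because the reaction is foreseen in the protocol and the change is cheap. It does not threaten the efficacy analysis.

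**What to change.** - **Capture (Protocol 9.2 and eCRF).** Require side as left, right, both or midline for every AE on the face or around the eyes, inside or outside the treatment area.
- **Tabulation (SAP 4.4.1).** Split the outside category into face on the LEO 43204 side, face on the vehicle side, face both/midline/undetermined, and elsewhere on the body. Show periorbital and eyelid events in this split whether they are classed as cutaneous or not.
- **Consistency.** Reconcile Protocol 9.2, Protocol 11.3.8 and SAP 4.4.1, so that the meaning of a by-treatment AE table is stated for events outside both areas.
- **Data already collected.** Query side from source records, and from photographs for cohorts 1 to 3.

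The cost is one mandatory field, one extra table split and a small number of queries. Bilateral, midline and gel-transfer events will stay ambiguous and should be shown as such, not forced into a treatment column. The change concerns recording and reporting only.

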9.2.1 Actions Taken as a Consequence of an AE

Action taken with trial treatment: Any action taken with trial medication as a consequence of the AE must be recorded (dose not changed, dose reduced, dose increased, drug interrupted, drug withdrawn, not applicable, unknown).

Other action taken: Any other action taken as a result of the AE must be recorded (none, concomitant medication, concurrent procedure).

Withdrawn due to AE: It must be recorded whether the AE leads to withdrawal from the trial.

9.3 Other Events to be Reported

9.3.1 Pregnancy

Any pregnancy occurring during the clinical trial must be reported to LEO within 24 hours of first knowledge using the (paper) Pregnancy Form (Part I). All such pregnancies must be

followed up until delivery or termination and final outcome must be reported on the (paper) Pregnancy Form (Part II) within 24 hours of first knowledge.

The completed Pregnancy Forms must be faxed or scanned and e-mailed to Global Pharmacovigilance, LEO (see section [9.4.1](#) for contact details).

Please also confer with section [7.7](#), Withdrawal Criteria.

